## PROTOCOL

### Background

#### 1. Provide the scientific background, rationale and relevance of this project.

Exogenous insulin therapy in individuals with Type 1 Diabetes is needed to compensate for the practically absent internal insulin secretion which follows from the autoimmune destruction of pancreatic  $\beta$ -cells. As a consequence, the quality of glucose control in Type 1 diabetes is heavily dependent on multiple daily treatment decisions by the patient, whose effect on blood glucose variability is mediated by individual glucose metabolism parameters, such as insulin sensitivity (SI) [1-4].

SI is a key parameter in the treatment of diabetes describing how sensitive the body is to the effects of insulin. In general, if someone has higher SI, the amount of insulin required to lower his blood glucose levels is smaller than that needed by someone who has low sensitivity. However, SI levels within the same person are not constant, and fluctuations of SI happen very frequently in the life of subjects with diabetes, e.g., in response to physical activity, making insulin dosing and therapy parameters very difficult to tune [5-12].

[figure not shown]
In such context, the purpose of the study is to demonstrate safety and feasibility of an SI-informed bolus calculator, aimed at improving insulin dosing by adjusting insulin boluses to the patient's sensitivity to insulin action at the time the bolus is administered. To modulate the insulin bolus, we first track the subject's SI fluctuations from continuous glucose monitor data, insulin, and meal records collected over several days of monitoring (e.g., 2 to 4 weeks). This allows us to build a 24-hour profile of SI for the subject, which represents the usual pattern of sensitivity to insulin action the subject shows across the day. At the time a bolus is administered, we then estimate the real-time subject's SI, and correct the bolus based on the ratio between usual SI at this time of day (from the profile) and real-time SI level. The SI-informed insulin bolus can be calculated as follows:

$$B_t^{SI} = \frac{SI_t^{PRF}}{SI_t} \left( \frac{\text{carbohydrate intake}}{\text{insulin-to-carbohydrate ratio}} + \frac{BG_t - \text{target } BG}{\text{correction factor}} + IOB_t^{\text{BASAL}} \right) - IOB_t^{\text{TOTAL}}$$

where the regular insulin bolus computed from insulin-to-carbohydrate ratio, correction factor and insulin on board (IOB), is modulated by the ratio of usual SI at time  $t$  ( $SI_t^{PRF}$ ) and real-time SI assessed at time  $t$  ( $SI_t$ ). The idea behind the bolus modulation is that insulin therapy parameters are tuned to account for the usual SI pattern, and do not account for acute changes of SI introduced, e.g., by physical activity. As seen from the formula, if  $SI_t = SI_t^{PRF}$ , the administered bolus will remain unchanged, while it will be increased/decreased if the subject is less/more sensitive than usual at the time the bolus is administered. The ratio used to modulate the bolus will be saturated in order not to allow modifications larger than 30% of the original bolus amount (this means that during the experimental admission the dose suggested by the computed bolus modulator will be between 70% and 130% of the standard dose indicated by the DiAs system using the participant's insulin therapy parameters). If this change of insulin dose is deemed not

to be safe by the licensed endocrinologist conducting this study, this insulin dose will not be administered and the standard dose calculated using the participant's insulin therapy parameters will be indicated for administration.

The proposed SI-informed bolus calculator has been tested *in silico* using the UVa/Padova Type 1 Diabetes Simulator - a simulation platform approved by the FDA as a substitute to preclinical trials in testing insulin treatments [13,14]. The platform consists of a mathematical model of differential equations describing glucose metabolism in Type 1 Diabetes and is equipped with a population of 100 *in silico* adult subjects with metabolic behaviors similar to those observed in individuals with Type 1 Diabetes. Resorting to the simulator, the scenario proposed for the Research Admissions of this study has been reproduced. A model of mild-to-moderate physical activity impact on glucose metabolism has been used to simulate the exercise session at the local gym. A dinner meal has been administered at 7PM following the exercise session, and the postprandial control obtained with the use of the SI-informed bolus calculator has been compared to the one obtained when the standard bolus calculator (or functional insulin therapy) was utilized. Postprandial (i.e., 6 hours following dinner) Low Blood Glucose Index (LBGI) and High Blood Glucose Index (HBGI) – glucose variability indicators used to quantify the exposure to hypo- and hyperglycemia, respectively [15,16] – have been computed from glucose sensor data. The number of hypoglycemia treatments administered in the same postprandial time interval has also been tracked. Figure 1 shows these metrics in bar graphs for the SI-informed bolus calculator (Experimental Admission [EX]) and standard bolus calculator (Control Admission [CON]). The use of the SI-informed bolus calculator decreased the total number of hypoglycemia treatments from 34 to 6 and allowed to considerably reduce LBGI (from 2.4 to 1.3) at the price of a minor increase in HBGI (from 0.17 to 0.18).

**Figure 1: LBGI, HBGI and number of hypoglycemia treatments in the 6 hours following the simulated controlled dinner meal using the SI-informed bolus calculator (EX) and the standard bolus calculator (CON).**

Also, an initial version of the SI-informed bolus calculator has been deployed as part of a CGM-informed decision support system, which showed reduction of glucose variability in individuals with Type 1 Diabetes using an insulin pump or multiple insulin injection [17].

Because of the known impact of physical activity on post-exercise SI fluctuation [18], the purpose of this study is to test the feasibility of using the SI-informed bolus calculator in a clinical trial, where it would be deployed for the control of one supervised meal following an afternoon exercise period.

The proposed intervention is an insulin bolus calculator based on continuous glucose monitoring and insulin/meal history. The glucose sensor used in the study (Dexcom G6) is FDA-approved for the non-adjunctive measurement of blood glucose and is the first to follow the interoperable continuous glucose monitoring (iCGM) guidelines and is “*to be used as part of an integrated system with other compatible medical devices and electronic interfaces, which may include automated insulin dosing system, insulin pumps, blood glucose meters, or other electronic devices used for diabetes management*” [19]. Under these guidelines, “*FDA recognized this as an opportunity to reduce the regulatory burden for this type of device by establishing criteria that would classify these as “moderate risk” class II medical devices*”. Furthermore, the proposed intervention results in a meal bolus that is presented to the user (the participant) and not automatically transferred to the injection device (the pump); the SI-informed bolus is also provided to the study MD for approval prior to use at the time of the one supervised meal. The study physician may overwrite the insulin dose computed with the use of the SI-informed bolus calculator at any time.

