**Figure 2: Example of web-based diabetes management systems used for data upload (Diasend top, CareLink bottom)**

### **Visit 3 and 4: Research Admission (i.e., Hotel).**

The Experimental and Control Admission will be separated by at least 48 hours with a maximum of 100 days. The order of these two visits will be randomly selected. Subjects will be admitted to the research location at approximately 9:00AM and will be discharged after approximately 24 hours.

All procedures will be the same for Visit 3 and Visit 4 with the following exception:

- Insulin Boluses during the Control Admission: All meal and correction boluses during the control admission will be per the subject's usual insulin parameters. The two admissions will use consistent insulin-to-carbohydrate ratio, correction factor, and basal profiles.
- Insulin Boluses during Experimental Admission: The dinner meal bolus will be determined with the use of the SI-informed bolus calculator during the Experimental Admission. The calculations will be performed on a study smartphone (Diabetes Assistant, DiAs), approved by the study MD, and subsequently communicated to the subject. The suggested insulin bolus will be administered through the subject's personal insulin pump. The study physician will override the insulin dose computed with the use of the SI-informed bolus calculator at any time if he/she considers it is not safe for the participant subject in the following way:

- 1 The dinner insulin dose suggested by the SI bolus calculator will be  $\pm 30\%$  of the dose that the subject should receive while using his/her own insulin pump bolus calculator (usual care). This is by design of the SI bolus calculator.
- 2 If the licensed endocrinologist conducting the study considers the dinner dose suggested by the SI bolus calculator to be unsafe he/she will override this dose.
- 3 In order to avoid bias between the physicians involved, every effort will be made to have the primary MD supervising all the experimental admission.

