- 4 Since the visits will be randomized, regardless of when the experimental visit occurs, the MD supervising the trial will look at the standard dose suggested by the DiAs system using the participant's insulin therapy parameters and will indicate that dose (control) if the assigned insulin dose suggested by the SI bolus calculator is deemed to be unsafe. This will be equal regardless of who is the physician supervising the visit. In this way any bias will be avoided since the criteria used by all MDs listed on this protocol will be the same.
- 5 During both visits, control and experimental, the same procedures will be followed. Therefore, the dose suggested by the DiAs system using the participant's insulin therapy parameters during the experimental admission to override the dose suggested by the SI bolus calculator, should be consider safe and usual care for that particular participant.

Visits 3 and 4 will be fully supervised by a research team located at the hotel and gym at all times and will be monitored and supervised by the primary physician. In the event that the primary physician could not be available for a particular visit, the backup MDs will cover. The team will consist of a minimum of one registered nurse (trained in the execution of the protocol as well as in the management of hypo- and hyperglycemia) and a technician (trained in the use and maintenance of the DiAs system). In addition, one of the study medical physicians, primary MD, and one senior engineer will be on call during the entire admission, with backup physicians and engineer available if the primary contact is unable to be reached.

The CGM used in the study is FDA-approved for the non-adjunctive measurement of blood glucose and will be remotely monitored in real-time during the entire admission (including exercise) by the study team via the DiAs Web Monitoring platform. The CGM readings will be the primary source of blood glucose levels. There are no protocol fingerstick blood glucose measurements other than at times of CGM calibration and if directed by the study team.

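### Do the printed bolus formula and the two descriptions of the reference dose undermine the 70%–130% limit on the experimental dinner dose?

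*Combined protocol and SAP*

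**What the plan says.** The Background (item 1) introduces the formula with "The SI-informed insulin bolus can be calculated as follows". The ratio of profile SI to real-time SI multiplies a bracket made up of the carbohydrate term, the correction term and basal IOB. Total IOB is then subtracted outside the bracket. When the two SI values are equal, "the administered bolus will remain unchanged".

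The limit comes next: "The ratio used to modulate the bolus will be saturated in order not to allow modifications larger than 30% of the original bolus amount". The same sentence explains in parentheses that "the dose suggested by the computed bolus modulator will be between 70% and 130% of the standard dose indicated by the DiAs system", computed from the participant's therapy parameters.

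Under Visit 3 and 4: Research Admission, item 1 on the experimental bolus again gives ±30%, but of "the dose that the subject should receive while using his/her own insulin pump bolus calculator (usual care"), and adds: "This is by design of the SI bolus calculator". On where the dose is produced, that section says: "The calculations will be performed on a study smartphone (Diabetes Assistant, DiAs), approved by the study MD, and subsequently communicated to the subject". Item 4 says the supervising physician "will look at the standard dose suggested by the DiAs system" and uses that dose if the SI-informed one is judged unsafe. Under Procedures at beginning of Research Visit, item 4 notes that DiAs is linked to the CGM and not to the pump.

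**The concern.** Two features catch the eye.

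First, the text after the formula describes the regular bolus, IOB included, as modulated by the ratio, whereas the formula leaves total IOB unscaled. A reader who takes the saturation to mean a ratio held between 0.7 and 1.3 will find that the printed formula can give a dose outside 70%–130%. Basal and total IOB are not defined. If total IOB includes the basal part, as the labels suggest, it would usually be above zero in a pump user, so this would not be a rare case. The afternoon exercise is meant to shift SI before dinner, so the ratio is expected to move away from 1.

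Second, the limit has two reference doses, DiAs in one place and the pump's own calculator in another. Nothing says that the two calculators return the same number, or how IOB reaches DiAs without a link to the pump.

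The 30% figure is the only numeric limit on the single experimental dose in a safety and feasibility trial. If it did not hold, the description of the intervention would be wrong on a safety point.

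**Working it through.** **Inputs.** From the documents: the formula, the 30% limit and the rule that a ratio of 1 leaves the bolus unchanged (Background, item 1). Not in the documents, and therefore assumed below: numeric limits on the ratio, the size of the standard dose, IOB values, and any difference between the DiAs and pump doses.

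**Algebra.** Let r be the SI ratio, T total IOB and S the standard dose (the formula at r = 1, taken as above 0). The bracket equals S + T, so

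dose = r(S + T) − T, and dose/S = 1 + (r − 1)(1 + T/S).

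**The stated range.** The 70%–130% cannot be derived from printed inputs alone, since no ratio limits or IOB values are given. It is recovered in any of three ways:

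- T = 0 with r between 0.7 and 1.3.
- r between 0.7 and 1.3 scaling the whole net bolus.
- r limited to 1 ± 0.3·S/(S + T). With S = 6 U and T = 1 U this is 1 ± 0.3 × 6/7, or 0.743 to 1.257. The doses are then (5.2/7) × 7 − 1 = 4.2 U (70%) and (8.8/7) × 7 − 1 = 7.8 U (130%).

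**The worrying case.** Assume instead that r is held at a fixed 0.7–1.3 in the printed formula:

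| S (U) | T (U) | Lowest dose | Highest dose | % of S |
|---|---|---|---|---|
| 6 | 0 | 4.20 | 7.80 | 70–130 |
| 6 | 0.5 | 0.7 × 6.5 − 0.5 = 4.05 | 1.3 × 6.5 − 0.5 = 7.95 | 67.5–132.5 |
| 6 | 1.0 | 0.7 × 7 − 1 = 3.90 | 1.3 × 7 − 1 = 8.10 | 65–135 |
| 6 | 1.5 | 0.7 × 7.5 − 1.5 = 3.75 | 1.3 × 7.5 − 1.5 = 8.25 | 62.5–137.5 |
| 6 | 2.0 | 0.7 × 8 − 2 = 3.60 | 1.3 × 8 − 2 = 8.40 | 60–140 |

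The excess is 0.3T at each end, or 0.15 to 0.60 U in the rows with IOB. It arises only when |r − 1| exceeds 0.3/(1 + T/S). At S = 6 U and T = 1 U that means r below 0.743 or above 1.257.

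**Which rule the text states.** The saturation sentence limits the change in the bolus and gives the resulting dose range. Visit 3 and 4, item 1 also puts ±30% on the dose. Neither puts a number on the ratio. Read plainly, the ratio is limited as far as needed to keep the dose within 30%, which is the third route above.

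**Reference dose.** If the DiAs standard dose were c times the pump dose, 70%–130% of the DiAs dose would be 70c%–130c% of the pump dose. At c = 0.95 this is 66.5%–123.5%, at c = 1.05 it is 73.5%–136.5%, at c = 0.90 it is 63%–117%, and at c = 1.10 it is 77%–143%. Every value of c here is assumed. The documents keep carbohydrate ratio, correction factor and basal profile consistent across admissions. Item 4 labels the DiAs dose as the control dose, and item 5 describes it as usual care for that participant.

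**The case for a change.** The strongest case for acting is that a numeric safety limit should be verifiable from the page, and this one is not. The prose and the formula treat IOB differently. The two IOB terms are undefined, and the two sections name different calculators. None of that depends on an assumption. Shared therapy parameters do not guarantee equal IOB, so the equivalence of the two standard doses is relied on without being shown. Physician approval is a real safeguard but sets no number. Tidying the text would cost only wording and a check of the DiAs code.

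These textual observations stand. The step from them to a fault in the plan does not. A breach needs a fixed ratio limit that the protocol does not state, and a gap between the two references needs a difference that the protocol does not report. A missing link between DiAs and the pump does not show that insulin data are unavailable to DiAs. As the admission is described, the SI-informed dose and the standard dose are both available on DiAs, and the physician sees them before anything is given. A departure beyond 30% of the DiAs dose would therefore be visible at that point. The dose is also not sent automatically to the pump.

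**Conclusion.** The algebra is right, but it rests on a fixed 0.7–1.3 ratio limit that appears nowhere in the protocol. Under that assumption, with a 6 U standard dose and 0.5 to 2 U on board, the overshoot would be 2.5 to 10 percentage points at each end. Under the rule as worded, which limits the change in the bolus, it is zero. What remains is an implementation detail that is not spelled out, plus a wording inconsistency over the reference dose. The Background and the Visit 3 and 4 section must be reconciled on that reference and on what is limited. Which version stands is for the clinical team, and no view is taken here.

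Nothing in the statistical plan changes. The primary comparison is LBGI after dinner, Experimental against Control Admission within the same participant, and it does not use the limit. The random order, the target of 15 completers and the planned Cohen's *d* do not depend on it either. The conclusion rests on the plain reading of the saturation sentence and on the absence of any documented DiAs–pump difference. The DiAs code is not in the documents, so its behaviour is neither confirmed nor faulted.

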### Objectives/Hypothesis

The primary aim of the research project is to demonstrate safety and feasibility of a new SI-informed bolus calculator, based on a continuous glucose monitor (CGM)-informed algorithm for the real-time tracking of SI. The SI-informed bolus calculator will be compared to standard therapy in terms of overall and postprandial occurrence of hypoglycemia as measured from CGM data using the Low Blood Glucose Index (a glucose variability measure and predictor of severe hypoglycemia, designed to aggregate the frequency and extent of low blood glucose events into a single number), which will be expected to be better when the optimized bolus calculator is used.

### Study Design: Biomedical

1. Will controls be used? Yes.

► IF YES, explain the kind of controls to be used.

Each participant will be his/her own control, participating in an experimental admission as well as a control admission.

**2. What is the study design?**

This is a single-center randomized crossover trial. We will target completion of 15 adults (age 18-65 years) with Type 1 Diabetes who use an insulin pump. Subjects will undergo an initial Screening Visit and randomization will occur if the visit is successfully completed. After completion of the Screening Visit, each subject will participate in an at home Data Collection Period that will last approximately 14 to 28 days while using their personal insulin pump, a personal glucometer, a study CGM, and a study activity tracker (i.e., Fitbit). This data collection period may be extended to gather more days of quality data, if needed per principal investigator judgement. Once the data has been collected and processed, subjects will participate in two 24-hour admissions (Experimental and Control Admission) in a semi-controlled environment (i.e., hotel), performed in the assigned random order. During both admissions, subjects will use their personal insulin pump and glucometer, and a study CGM. Subjects will be admitted around 9AM. Subjects will be advised to have their home breakfast per their normal routine; around 12PM, they will be provided lunch, followed by an exercise session around 2:30PM. The exercise session will consist of three 15-minute bouts of moderate-intensity exercise (i.e., stationary bicycle). Around 7PM, subjects will be provided a controlled dinner; the SI-informed bolus calculator will be used in the Experimental Admission while standard therapy will be used in the Control Admission. Subjects will then be observed overnight and discharged in the following morning.

**3. Does the study involve a placebo? No**

**► IF YES, provide a justification for the use of a placebo**

**Human Participants**

**Ages:** 18-65

**Sex:** Male and Female

**Race:** All

**Subjects- see below**

**1. Provide target # of subjects (at all sites) needed to complete protocol.**

Fifteen (15) subjects are needed to complete the study.

**2. Describe expected rate of screen failure/dropouts/withdrawals from all sites.**

Because of the length of the study, we expect an approximately 40% rate of dropouts/withdrawals from the study.

**3. How many subjects will be enrolled at all sites?**

This is a single site clinical trial to be completed at UVa. Given the potential of a 40% dropouts/withdrawals rate, up to 25 people will be enrolled.

**4. How many subjects will sign a consent form under this UVa protocol?**

This study will have up to 25 subjects sign the consent form with the goal of completing 15 study subjects.

## Inclusion/Exclusion Criteria

### 1. List the criteria for inclusion

1. Type 1 diabetes for at least 12 months
2. Current use of an insulin pump for at least 12 months
3. Current or historical use of a CGM system for at least 6 months
4. Age  $\geq 18$  to  $\leq 65$  years old
5. HbA1c  $< 8.5\%$  at screening; if HbA1c  $< 6.0\%$  then total daily insulin must be  $\geq 0.5$  U/kg
6. For females, not currently known to be pregnant. If female and sexually active, must agree to use a form of contraception to prevent pregnancy while a participant in the study. A negative urine pregnancy test will be required for all premenopausal women who are not surgically sterile. Subjects who become pregnant will be discontinued from the study
7. Willingness to use the same set of insulin therapy parameters (i.e., basal rate, insulin-to-carbohydrate ratio, correction factor) during both admissions
8. Willingness to upload data during the study
9. An understanding of and willingness to follow the protocol and sign the informed consent

### 2. List the criteria for exclusion

1. Diabetes ketoacidosis (DKA) in the 6 months prior to enrollment
2. Clinically significant electrocardiogram (ECG) found at Screening as determined by the study medical physician
3. Severe hypoglycemia resulting in seizure or loss of consciousness in the 6 months prior to enrollment
4. Currently being treated for a seizure disorder
5. Coronary artery disease or heart failure, unless written clearance is received from a cardiologist or primary care provider and documentation of a negative stress test within the year
6. History of cardiac arrhythmia (except for benign premature atrial contractions and benign premature ventricular contractions which are permitted)
7. Cystic fibrosis
8. Pregnancy, breast-feeding, or intention of becoming pregnant over time of study procedures
9. Abnormal liver function test results (Transaminase  $> 2$  times the upper limit of normal)
10. Abnormal renal function test results (calculated GFR  $< 60$  mL/min/1.73m^2)
11. Uncontrolled thyroid disease (TSH undetectable or  $> 10$  mIU/L)
12. A known medical condition that in the judgment of the investigator might interfere with the completion of the protocol such as the following examples:
  - Inpatient psychiatric treatment in the past 6 months for either the subject or the subject's care companion
  - Presence of a known adrenal disorder
  - Active gastroparesis

- If on antihypertensive, thyroid, anti-depressant or lipid lowering medication, lack of stability on the medication for the past 2 months prior to enrollment in the study
- 13. Abuse of alcohol or recreational drugs
- 14. Infectious process not anticipated to resolve prior to study procedures (e.g. meningitis, pneumonia, osteomyelitis)
- 15. Uncontrolled arterial hypertension (Resting diastolic blood pressure >90 mmHg and/or systolic blood pressure >160 mmHg)
- 16. A recent injury to body or limb, muscular disorder, use of any medication, any carcinogenic disease, or other significant medical disorder if that injury, medication or disease in the judgment of the investigator will affect the completion of the protocol
- 17. Basal Rate <0.01 units/hour
- 18. Inability to be physically active for more than 30 minutes per day
- 19. Conditions that would make use of a CGM difficult (e.g., blindness, severe arthritis, immobility)
- 20. Current enrollment in another intervention clinical trial

